1. PROJECT TITLE

Right Ventricular Hemodynamics using Cardiac MRI in COPD Patients with OSA

3. FACILITIES

UCSD, Clinical Teaching Facility – Sleep Laboratory

4. ESTIMATED DURATION OF THE STUDY

July 2014 through June 2016

5. LAY LANGUAGE SUMMARY OR SYNOPSIS (no more than one paragraph)

The coexistence of chronic obstructive pulmonary disease (COPD) and obstructive sleep apnea (OSA) in the same patient has been termed overlap syndrome, affecting 1% of the U.S. population. Despite the high prevalence of overlap syndrome, few data are available on its pathophysiological and clinical consequences. Overlap syndrome has recently been reported to have excess mortality compared with COPD alone. Thus study of overlap syndrome patients may be useful toward understanding the underlying pathways. No study has evaluated the mechanisms of excess cardiovascular mortality in untreated overlap syndrome. Also, no prospective, randomized, controlled data are available on treatment of overlap syndrome. Thus, we propose to conduct this prospective, randomized, controlled pilot study that aims: (1) to compare right and left ventricular hemodynamic parameters using cardiac MRI in overlap syndrome vs. COPD only and OSA only; (2) to compare the effects of bi-level positive airway pressure (BiLevelPAP) vs. nocturnal oxygen therapy (NOT) on right ventricular (RV) hemodynamics in overlap syndrome. This will allow us to test the hypothesis that treatment of both hypoxemia and hypercapnia during sleep will improve RV hemodynamics compared with treatment of hypoxemia alone in patients with overlap syndrome. Potential benefits to patients and society will include better understanding of the mechanisms of cardiovascular mortality in overlap syndrome. We believe that these data will encourage use of PAP therapy in COPD patients with overlap syndrome if we observe significant improvement. We also plan a larger multi-center trial if this study provides encouraging preliminary data.

6. SPECIFIC AIMS

Study Aims:

- a) To compare right and left ventricular (LV) hemodynamic parameters using cardiac MRI in overlap syndrome vs. COPD only and OSA only in a cross-sectional study;
- b) To explore mechanisms of cardiovascular dysfunction in overlap syndrome;
- c) To conduct a pilot clinical trial to compare the effects of BPAP vs. nocturnal oxygen therapy (NOT) on RV hemodynamic parameters in overlap syndrome (20 subjects in each arm) to establish feasibility.

We hypothesize that:

- a) Patients with overlap syndrome have more RV dysfunction than those with COPD only or OSA only;
- b) Treatment of both hypoxemia and hypercapnia plus catecholamine surges will improve RV hemodynamic parameters compared with treatment of hypoxemia alone in patients with overlap syndrome.

7. BACKGROUND AND SIGNIFICANCE

Prevalence and clinical significance of overlap syndrome

COPD and OSA are both common diseases affecting 10-20% and 5% respectively of the adult population over 40 years of age². Both disorders carry considerable morbidity and mortality. Their coexistence in the same patient, termed overlap syndrome, is a common occurrence and may affect 1% of the U.S. population. A prospective, observational study found that all-cause mortality was 42.2% in the untreated (no CPAP) overlap syndrome group, significantly higher than in the COPD-only group (24.2%) after a median follow-up of over 9 years. Overlap syndrome is also associated with higher a risk of hospitalization for COPD exacerbation (relative risk 1.70) compared with COPD-only patients. Thus, it is important to know the mechanisms of mortality and the optimal treatment modality in this common disease.

Pulmonary hypertension (PH) and RV dysfunction in overlap syndrome

The high mortality in untreated overlap syndrome patients is due to cardiovascular mortality, but the exact mechanisms are not yet known. However, some evidence suggests that pulmonary vasoconstriction and RV dysfunction may be an underlying mechanism. The prevalence of PH in overlap syndrome is much higher than in OSA alone. PH and RV dysfunction are associated with poor prognosis in COPD. The 5-year survival rate is only 36% in those whose initial mean pulmonary artery pressure (mPAP) is >25 mm Hg compared with 66% in those whose initial mPAP is <25 mm Hg. Moreover, severity of PH correlates negatively with survival (5-year survival ~15% with mPAP > 40 mm Hg vs ~55% with mPAP 20–40 mmHg). On the other hand, RV dysfunction and hypertrophy have also been described in otherwise uncomplicated OSA (figure 2). Although RV function can be abnormal in either disease, it may be worse in overlap syndrome due to the increased burden of hypoxemia and hypercapnia. However, the changes in RV function have not been well studied in patients with overlap syndrome. In addition, endothelial dysfunction of pulmonary vasculature plays an integral role in the pathogenesis of pulmonary hypertension (PH). The gold standard for early detection of endothelial dysfunction requires intracoronary or intra-brachial infusions of vasoactive agents. However, it is invasive with potential side effects of vascular or nerve injuries. Recently, several non-invasive techniques have been developed to assess endothelial function and one of them is peripheral arterial tonometry (PAT) in response to reactive hyperaemia. This technique evaluates the percentage change of flow from baseline to the maximum flow during reactive hyperaemia following a five minute ischemia of the distal forearm (achieved by blowing up a blood pressure cuff around the arm). The advantage of this technique is non-invasive, simple, and reproducible with less observer dependence comparing to ultrasound based technique. Therefore, we choose to use this technique to evaluate the endothelial function in this study. Furthermore, recognizing that COPD and OSA are both important contributors to secondary PH, clinicians would likely treat both underlying diseases. With COPD, long-term oxygen therapy can improve COPD mortality. In OSA, continuous PAP (CPAP) therapy can improve PH. However, there is no rigorous research on how patients with overlap syndrome should be treated.

Rationale for using cardiac MRI to measure cardiac hemodynamic parameters

One way to measure the short term impact of any therapy on the cardiovascular system is with cardiac magnetic resonance imaging (MRI), which has been shown to be sensitive in measuring RV hemodynamic parameters. Furthermore, cardiac MRI findings correlate with clinical changes and can have prognostic value in PH. Compared to standard, 2–dimensional echocardiography, cardiac MRI has been shown to be superior in detecting regional wall motion abnormalities, RV function, size and muscle mass. Cardiac MRI also offers advantages over echocardiography since obesity or emphysema do not interfere with the MRI image quality and thus interpretation. A recent pilot study using cardiac MRI demonstrated RV remodeling in overlap syndrome patients compared with COPD patients, further confirming the utility of this modality. Another pilot study detects early fibrosis changes of extracellular volume (ECV) mapping techniques in COPD patients. Thus, we believe that cardiac MRI may be the preferred technique to assess pulmonary hemodynamics and RV function in patients with COPD and OSA overlap syndrome.

Overlap Syndrome and Upper Airway Inflammation

Obstructive sleep apnea is characterized by a recurrent collapse of the upper airway which has been shown to be associated with an increase inflammatory cells in surgical samples from the uvula, pharyngeal and nasal mucosa, and upper airway muscle. COPD is also characterized chronic inflammation of upper and lower airways, which was initially triggered by smoking. Since recent evidence demonstrated that exacerbation of COPD is associated with increased inflammation of both upper and lower airways, upper airway inflammation from OSA in patients with overlap syndrome (coexistence of OSA and COPD) may contribute to worse COPD prognosis comparing to patients with COPD alone. However, there is limited research in upper airway inflammation of patients with overlap syndrome at present time and more research is warranted. A minimally invasive technique, pharyngeal lavage, has been recently developed to assess mucosal inflammation of the upper airways in normal, OSA, and heavy snoring patients. With this new technique, we believe that we could further characterize the upper airway inflammation and potential pathophysiology in patients with overlap syndrome.

Positive airway pressure therapy in COPD

Treatment of hypoxemia in COPD alone has been shown to improve mortality. However, treatment of hypercapnia in COPD with nocturnal Bilevel has shown contradictory results. Of note, known OSA was excluded from the bulk of these above cited COPD studies. We postulate that COPD patients with concomitant OSA may be ideal candidates for positive pressure ventilation, since this intervention could treat both hypoxemia and hypercapnia.

Positive airway pressure therapy in overlap syndrome

Overlap syndrome patients are typically hypercapnic at more preserved levels of lung function than those with COPD alone (average forced expiratory volume in one second, FEV1 1.8 vs. 1.0 L). Therefore, overlap syndrome patients are likely to be particularly susceptible to pulmonary artery vasoconstriction due to intermittent hypoxemia and hypercapnia. OSA causes pharyngeal obstruction resulting in intermittent hypercapnia and hypoxemia. Accessory respiratory muscle atonia during REM sleep in patients with underlying COPD commonly leads to hypercapnia. By decreasing hypoxemia and hypercapnia, with resultant reduction of pulmonary artery vasoconstriction, treatment of overlap syndrome at night may well improve RV

(and LV) performance during the daytime. One uncontrolled study showed an improvement in gas exchange and FEV1 with CPAP therapy in overlap syndrome. Another prospective study showed a reduction in mortality and hospitalizations due to COPD exacerbations after CPAP therapy in overlap syndrome. Furthermore, we recently observed in 11,000 patients improved mortality in a dose response relationship with CPAP use in patients with overlap syndrome, although again lack of randomization limits definitive conclusions. To date, no prospective, randomized, controlled study has yet evaluated the effect of BiLevel therapy on clinical outcomes in overlap syndrome.

Rationale for using BiLevel vs. NOT

BiLevel can treat both hypoxemia and hypercapnia. We will use BiLevel to treat OSA in COPD patients rather than conventional CPAP therapy because COPD patients are prone to hypoventilation during sleep (especially REM sleep) due to atonic accessory respiratory muscles. Nocturnal oxygen therapy (NOT) corrects nocturnal hypoxemia. NOT will be used in the control group because recurrent transient hypoxemia during sleep is frequent in patients with COPD, and nocturnal desaturation during sleep is an independent risk factor for increased cardiovascular complications. Previous studies of oxygen therapy in COPD have shown that NOT is safe, even in hypercapnic COPD patients. CPAP, however, has less predictable effects on hypoxemia or hypercapnia in overlap syndrome patients. Thus, by comparing BiLevel vs. NOT, we can independently assess the effect of sleep-related hypercapnia on RV hemodynamics. Also, it will allow us to test the hypothesis that treatment of both hypoxemia and hypercapnia will improve RV hemodynamic parameters compared with treatment of hypoxemia alone in patients with overlap syndrome.

Limitations of prior literature

Though it is known that untreated overlap syndrome has increased cardiovascular mortality compared to COPD, the mechanisms of cardiovascular dysfunction in overlap syndrome have not been studied. Moreover, prospective, randomized, controlled trials of BPAP therapy in overlap syndrome are lacking. Our study will provide insight into mechanisms of excess cardiovascular mortality in overlap syndrome. The interventional part of our study is a pilot study to help determine optimal treatment of overlap syndrome patients. The preliminary data, if encouraging, will be used to plan a larger multi-center clinical trial with longer duration of BiLevel therapy (with mortality, hospitalizations and COPD exacerbations as outcomes).

8. PROGRESS REPORT

N/A

9. RESEARCH DESIGN AND METHODS

Part One Study Objective: The first part is a cross-sectional cohort study comparing subjects with overlap syndrome to those with COPD alone and those with OSA alone.

Subjects: Our target sample will be 150 subjects in the overlap syndrome group. This group will include subjects with age > 18 years with known or suspected diagnosis of overlap syndrome, which we will define as COPD: Global Obstructive Lung Disease (GOLD) stage 2 disease or higher and OSA: apnea-hypopnea index (AHI) >15/hour. We will exclude patients already using oxygen or BiLevel/CPAP, patients with known or suspected renal failure (creatinine >1.5 mg/dl), pregnant women (due to possible risk to the fetus due to cardiac MRI and gadolinium contrast), patients with atrial fibrillation or frequent (>10/h) premature ventricular contractions (since these may complicate cardiac MRI sequences) and patients with known contraindications to

MRI: metallic (ferromagnetic) implants, cardiac pacemakers, past history of claustrophobia.

The control subjects will be divided into two groups, one with COPD only (50 subjects) and the other with OSA only (50 subjects). The COPD control group will include subjects with known COPD diagnosed by a pulmonologist (GOLD stage 2 or higher). The OSA control group will include subjects with a known diagnosis of OSA diagnosed by a sleep specialist (apnea-hypopnea index, AHI >15/hour). The exclusion criteria for the control subjects will be the same as the overlap syndrome subjects.

Study enrollment: All patients will be recruited through the outpatient pulmonary and sleep medicine clinics at the UCSD hospitals. Poster advertisements will be placed in the outpatient clinics to encourage subject recruitment through physician referral. COPD patients in outpatient pulmonology clinics who express interest in enrolling in the study will be approached by one of the study investigators to obtain informed consent. COPD patients meeting eligibility criteria will be screened for OSA risk and scheduled for overnight polysomnography (PSG) as part of baseline visit. COPD patients with coexisting OSA will be enrolled in the overlap syndrome group. COPD patients without coexisting OSA will be enrolled in the COPD only control group. If COPD patients are referred for clinically indicated sleep studies, these patients will also be eligible for participation (as either COPD only or overlap syndrome patients), depending on the results of the sleep study.

Baseline visit: At the baseline visit, all 3 groups (overlap syndrome, COPD only and OSA only) will undergo a baseline PSG and measurement of body weight and height to calculate body mass index (BMI). Cardiac MRI will be done to measure RV and LV hemodynamics. Data regarding RV function with RVEDV (primary endpoint), RVESV, RVEF, RV mass index, right atrial pressure, PA pressure and blood flow, indices of RV geometry, thickness and interdependence, as well as LV function including LVEDV, LVESV, LVEF, LV mass index, LV wall motion, extracellular volume (ECV) and coronary blood flow will be collected. Phlebotomy will be done to take blood samples for complete blood cell counts (with differentials), renal profiles, venous gas analysis, and exploratory analyses of inflammatory biomarkers and cytokines (CRP, TNF-alpha, IL-6, P-selectin, ICAM-1). Overnight urine samples will be collected to measure catecholamine excretion levels (epinephrine, norepinephrine, metanephrine, normetanephrine). Endothelium function will be evaluated through the non-invasive finger probes of the EndoPAT 2000 device (Itamar Medical, Caesarea, Israel). EndoPAT device measures digital pulse amplitude with the probes placed on the tips of both index fingers in reaction to temporary occlusion of arterial blood flow (achieved by blowing up a blood pressure cuff around the arm) for 5 minutes. Assessment of exercise capacity will be done using six-minute-walk-distance (6MWD) test. Saint George Respiratory Questionnaire (SGRQ) score and SF-36 Questionnaire will be used to assess health-related quality of life (HRQOL). The modified Medical Research Council (MMRC) score will be used to assess severity of dyspnea. The Epworth Sleepiness Scale (ESS) and Pittsburg Sleep Quality Index (PSQI) will be used to assess sleep quality and relevant symptoms. Assessment of upper airway inflammation will be done with a minimally invasive technique, pharyngeal lavage, immediately before and after the sleep study. To collect pharyngeal lavage samples, subjects simply gargle 45 ml of sterile saline in 15 ml increments for 10 seconds, then spit the saline for collection and analysis. The pharyngeal lavage fluid will be used to analyze cell counts with differential and the remaining will be frozen for later analysis of inflammatory biomarkers. Assessment of cognitive function will be done using psychomotor vigilance task (PVT) and motor sequence task (MVT) by a computer program. Pulmonary function tests (PFTs) will be performed using the American Thoracic Society (ATS) criteria. BODE index (COPD mortality risk index predictor) will be calculated from these parameters listed above. The MRI will be scheduled as soon as available after the overnight sleep study. The time commitment for the sleep study will be 10 hours. The time commitment for the pulmonary function test will be 1 hour. The time commitment for the MRI is typically 30-40 minutes. In total, the time commitment to complete all of the required procedures of the Baseline Visit is approximately 12 hours.

Part Two Study Objective: The second part of the study is a prospective, parallel-group, randomized, controlled pilot study examining the effect of BiLevel therapy (and NOT if needed) vs. NOT alone in patients with overlap syndrome (20 subjects in each treatment arm).

Study Intervention: This will be done in 40 subjects in overlap syndrome group only who provide informed consent (20 subjects in each treatment arm). Randomization of overlap syndrome subjects to nocturnal BiLevel therapy (plus oxygen if needed based on saturations <88% while on stable bi-level settings), and NOT only will be done using sequentially-numbered, opaque, sealed envelopes using 1:1 allocation ratio. Regular therapy with COPD medications including long-acting anticholinergic medications and inhaled corticosteroids will be continued as advised by the treating pulmonologist. Only COPD subjects with stable clinical course during the duration of study intervention will be called for follow-up visits as any COPD exacerbations during the course of study intervention may potentially confound the follow-up study results. The time commitment for this initial visit will require up to 2-3 hours of the subjects time.

Follow-up visits: The first follow-up visit will be done 2 weeks after starting treatment to ensure compliance and determine any discomforts due to treatment. At this visit phlebotomy will be done to take blood samples for venous gas analysis. Subjects will be asked to complete all questionnaires as outlined in the baseline visit. Second follow-up visit will be done 3 months after starting treatment to ensure compliance with treatment and determine any study related discomforts. Subjects will be asked to complete all questionnaires and cognitive function testing as outlined in the baseline visit. The final follow-up visit will be done 6 months after starting study treatment. Throughout the course of the study, regular telephone contact will be maintained by the study staff to ensure adherence to therapy and to address issues as they arise. At this final follow-up visit, all the tests done at baseline visit (except PSG) will be repeated as well as all afore mentioned questionnaires and cognitive function testing. This pilot study will generate preliminary data for a multi-center clinical trial with longer duration of PAP therapy and mortality, hospitalizations or COPD exacerbations as outcomes, if we find encouraging results. If the subject is called for follow-up visits, first follow up visit will require a time commitment of 15-20 minutes (2 week mark of starting treatment) for and the other two follow up visit will require a time commitment of 25-30 minutes (one at the 3-month mark of starting treatment and one final follow up visit). During the course of the 2 week, 3 month and 6 month periods between follow up visits, study staff may contact the patient to ensure adherence to therapy and address issues as they arise. While these phone call encounters may vary in time based on the subject's needs, typically they should require no more than 5-10 minutes of the subject's time.

Study endpoints: Primary endpoint: RVEDV (estimated by cardiac MRI) across the three study groups, and following intervention in the overlap syndrome patients in the randomized trial. Secondary endpoints: RVESV, RVEF, RV mass index, right atrial pressure, PA pressure and blood flow, indices of RV geometry, thickness and interdependence, LVEDV, LVESV, LVEF, LV wall motion, , extracellular volume, coronary blood flow, endothelial function (EndoPAT), serum complete blood cell counts (with differentials), serum renal profiles, pharyngeal lavage cell counts and differentials, serum and pharyngeal lavage inflammatory biomarkers (CRP, TNF-alpha, IL-6, P-selectin, ICAM-1), sympathetic activity (measured by urinary catecholamine excretion), HRQOL score and BODE index.

To offset transportation costs, parking costs and use of the volunteer's time, subjects will receive \$150.00 for the overnight sleep study and an additional \$100.00 for the MRI for a total of \$250.00 upon completion of all tests in Part I. Study staff might ask the subject to return for a second overnight sleep study visit in the event the

data is of poor signal quality or we were unable to obtain sufficient data to complete analysis. If the subject agrees to return for a repeat study, he/she will be compensated \$150.00 for their time and transportation.

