10. HUMAN SUBJECTS

We anticipate recruiting a total of 150 patients for phase one study: 50 patients with overlap syndrome, 50 patients with COPD, and 50 patients with OSA, age and gender matched to the overlap syndrome patients. For the phase two study, we aim to recruit 40 patients among the overlap syndrome patients who participated in phase one.

Phase One Study:

This group will include subjects with age > 18 years with known or suspected diagnosis of overlap syndrome, which we will define as COPD: Global Obstructive Lung Disease (GOLD) stage 2 disease or higher and OSA: apnea-hypopnea index (AHI) >15/hour. We will exclude patients already using oxygen or BiLevel/CPAP, patients with known or suspected renal failure (creatinine >1.5 mg/dl), pregnant women (due to possible risk to the fetus due to cardiac MRI and gadolinium contrast), patients with atrial fibrillation or frequent (>10/h) premature ventricular contractions (since these may complicate cardiac MRI sequences) and patients with known contraindications to MRI: metallic (ferromagnetic) implants, cardiac pacemakers, past history of claustrophobia. The control subjects will be divided into two groups, one with COPD only (50 subjects) and the other with OSA only (50 subjects). The COPD control group will include subjects with known COPD diagnosed by a pulmonologist (GOLD stage 2 or higher). The OSA control group will include subjects with a known diagnosis of OSA diagnosed by a sleep specialist (apnea-hypopnea index, AHI >15/hour). The exclusion criteria for the control subjects will be the same as the overlap syndrome subjects.

Phase Two Study:

40 patients in overlap syndrome group recruited during phase one study will be invited to participate in phase two study. The overlap syndrome patients who provide informed consent will be randomized into the two treatment arms (20 subjects in each treatment arm).

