14. POTENTIAL RISKS

As we anticipate minimal risk from our studies, we doubt any subject will need to be removed or excluded from the study.

There is a very small risk of loss of subject confidentiality. We will protect all subject information to the best

of our ability so this will not happen.

Phase One Study

We believe the risks and discomforts to be small. All patients will be screened for standard contraindications (e.g. implanted device and foreign bodies) for cardiac MRI. If contraindicated, patients will not be enrolled to the study. All participants will be given a full description of the risks associated with MRI scanning as part of informed consent process. Gadolinium contrast, which is required for cardiac MRI, has been associated rarely with the syndrome of nephrogenic systemic fibrosis in patients with moderate to severe kidney diseases. Therefore, moderate or severe kidney disease is one of the exclusion criteria to minimize the potential risk. Small number of patients may experience anxiety or claustrophobia due to the confined space of MRI scan. However, the anxiety or claustrophobia often, if not always, resolves after termination of the scan. We and other investigators have accomplished similar studies without incident.

Phase Two Study

We believe the risks and discomforts to be small. All patients will be screened for standard contraindications (e.g. implanted device and foreign bodies) for cardiac MRI. If contraindicated, patients will not be enrolled to the study. All participants will be given a full description of the risks associated with MRI scanning as part of informed consent process. Gadolinium contrast, which is required for cardiac MRI, has been associated rarely with the syndrome of nephrogenic systemic fibrosis in patients with moderate to severe kidney diseases. Therefore, moderate or severe kidney disease is one of the exclusion criteria to minimize the potential risk. Small number of patients may experience anxiety or claustrophobia due to the confined space of MRI scan. However, the anxiety or claustrophobia often, if not always, resolves after termination of the scan. We and other investigators have accomplished similar studies without incident. Nocturnal oxygen therapy (NOT) and BPAP therapy have both been used in COPD patients in numerous previous research studies without significant reportable risks. NOT and BiLevel therapy will be closely followed and titrated to minimize any discomfort or adverse effects.

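### Section 9 sets the overlap-syndrome target at 150, while Section 10 sets it at 50 within a Part One total of 150; the two cannot both hold

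*Protocol*

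**What the plan says.** Two sections of the protocol state how many people Part One, the cross-sectional comparison, will enrol.

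- **Section 9 (Research Design and Methods), Part One, Subjects:** "Our target sample will be 150 subjects in the overlap syndrome group". The controls are then listed separately: "one with COPD only (50 subjects) and the other with OSA only (50 subjects"). No Part One total is printed there.
- **Section 10 (Human Subjects):** "a total of 150 patients for phase one study: 50 patients with overlap syndrome, 50 patients with COPD, and 50 patients with OSA". The controls are to be matched to the overlap patients on age and gender.

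For Part Two, the randomised pilot, the sections agree. Section 9 says "This will be done in 40 subjects in overlap syndrome group only who provide informed consent", with 20 per arm. Section 10 says "we aim to recruit 40 patients among the overlap syndrome patients who participated in phase one", again with 20 per arm.

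**The concern.** The same group has two recruitment targets that differ threefold. The two sections describe the same study: Section 10 repeats Section 9's definition of overlap syndrome, its exclusions and its control groups almost unchanged.

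Section 9 names RVEDV across the three groups as the primary endpoint of this part, so the disputed number is the planned size of a primary comparison. Three things depend on it:

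- **Burden on subjects.** Section 9 puts the baseline visit, which includes an overnight sleep study, at about 12 hours. Section 14 adds: "Gadolinium contrast, which is required for cardiac MRI".
- **Shape of the comparison.** The groups are either 1:1:1 or 3:1:1, which bears on precision and on how the age and gender matching can work.
- **Uptake needed for Part Two.** All 40 randomised subjects come from the overlap group, so its size fixes what share of them must agree to take part.

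**Working it through.** **Inputs from the protocol**

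| Item | Section 9 | Section 10 |
|---|---|---|
| Overlap syndrome | 150 | 50 |
| COPD only | 50 | 50 |
| OSA only | 50 | 50 |
| Part One total | not printed | 150 |
| Part Two | 40 (20 per arm) | 40 (20 per arm) |

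**Step 1. Reproduce the stated total.** Section 10: 50 + 50 + 50 = 150, which matches its printed total. Section 10 is consistent with itself.

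**Step 2. Sum Section 9.** 150 + 50 + 50 = 250. This does not match 150.

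**Step 3. Size of the gap.** 250 − 150 = 100 subjects, and 250/150 − 1 = 67%. The whole gap lies in the overlap group, where 150/50 = 3.

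**Step 4. Look for a reading that reconciles them.**
- *A number screened rather than enrolled?* Section 9 calls 150 the target sample in the overlap group. COPD patients found not to have OSA go to the COPD-only group, so 150 cannot be a pool that contains them.
- *Different studies?* No. The definitions and control groups are the same.
- *Superseded text?* No. Both statements are body text of a protocol that carries one version date.

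**Step 5. What the gap means in practice, if 150 is intended.** With "the time commitment to complete all of the required procedures of the Baseline Visit is approximately 12 hours", 100 × 12 h = 1,200 hours, with 100 more sleep studies and 100 more contrast MRIs. The study period is "July 2014 through June 2016", or 24 months. Simple averages over that whole period are 250/24 = 10.4 and 150/24 = 6.3 Part One subjects per month. These are not planned rates. The period also has to hold Part Two's six-month follow-up, and no separate Part One recruitment period is given.

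**Step 6. Uptake for Part Two.** 40/150 = 27%, or 40/50 = 80%.

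**Step 7. Precision, as illustration only.** The protocol gives no alpha or power. Assume a two-sided two-sample t-test of overlap against one control group of 50, with 80% power. In the normal approximation the detectable difference in SD units is (z for alpha + z for power) × √(1/n + 1/50). At alpha 0.05:
- n = 50: (1.960 + 0.842) × √(1/50 + 1/50) = 2.802 × 0.200 = 0.56
- n = 150: 2.802 × √(1/150 + 1/50) = 2.802 × 0.1633 = 0.46

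The exact noncentral-t values are:

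| | 150 vs 50 | 50 vs 50 |
|---|---|---|
| Detectable difference, alpha 0.05 | 0.46 SD | 0.57 SD |
| Detectable difference, alpha 0.025 (split over two control comparisons) | 0.51 SD | 0.62 SD |
| Power at a true 0.46 SD, alpha 0.05 | 80% | 62% |

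**The case against.** The best case on the other side is that this is a slip of the pen with an evident answer. Section 10 is the only place that prints a total; it lists all three groups and adds up. Section 9's 150 equals that total exactly, as if the total had been attached to the wrong group. On that reading the intended number is 50, no extra burden arises and one sentence needs correcting. The randomised comparison is untouched, since either value supplies 40 overlap subjects.

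Much of this stands. The slip is the likeliest explanation, and the added hours and scans arise only if 150 is meant. Neither section contains a failed sum, so this is a conflict between two statements rather than an arithmetic error within one. The power figures rest on assumptions and prove nothing about the conflict.

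What does not follow is that the matter is settled. The protocol does not say which section governs, and a reader who follows Section 9 would recruit 100 more people than one who follows Section 10. The likely explanation is an inference that only the sponsor can confirm.

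A further fair point concerns matching. With 150 overlap subjects and 50 per control group, one-to-one matching is impossible. Section 10 does not say that the matching is one-to-one, so this is no second contradiction, but the matching statement would need a look if 150 is confirmed.

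**Conclusion.** The contradiction is real and must be corrected. The overlap group is 150 in Section 9 and 50 in Section 10; Part One is 250 by Section 9's numbers and 150 by Section 10's, a difference of 100 subjects (67%). This conclusion rests only on the printed group sizes and needs no assumption.

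The size of the cross-sectional RVEDV comparison is therefore undefined in the protocol. In the illustration above, the choice moves the detectable difference from 0.46 to 0.57 SD at alpha 0.05. The randomised comparison keeps its 20 per arm either way. What changes for Part Two is the room for refusals: an 80% uptake leaves little, a 27% uptake leaves a good deal.

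**What to change.** The sponsor confirms the intended overlap target, and Sections 9 and 10 then state the same overlap number and the same Part One total.

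- **If 50 is intended:** Section 9 should give 150 subjects in total, of whom 50 are in the overlap group. Section 10 stays as it is.
- **If 150 is intended:** Section 10 should give 250 in total, made up of 150 overlap, 50 COPD-only and 50 OSA-only. Its sentence on age and gender matching should then be checked against a 3:1:1 design.

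The cost is about one sentence in one section, plus the matching check in the second case. No endpoint and no Part Two number changes.
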